1) Protocol Title

Subdissociative Dose Ketamine for Treatment of Acute Pain in Subjects with Chronic Pain: A Randomized Controlled Trial

2) HSC Review History

This protocol has not been reviewed by any external HSC.

3) Investigator [name], MD [name] [name], MD [name] [name] [name]

4) Objectives*

This is a prospective, randomized, physician and subject blinded controlled clinical trial. This will be conducted to determine whether sub-dissociative dose Ketamine can improve pain control in subjects with chronic pain syndrome presenting to the emergency department with exacerbation of their chronic pain. We also aim to determine whether use of SDDK can reduce the amount of subsequent opioid pain medications required for adequate pain relief in this subject population. We hypothesize that there will be a statistically significant decrease in pain using SDDK versus placebo and subjects will require overall less opioid pain medications for adequate pain relief.

5) Background*

Pain management is a significant issue for many subjects presenting to the Emergency Department (ED) as increasing numbers of subjects present with this complaint. In the ED, treatment of acute pain is a primary concern both for the provider and the subject; recent data suggest that visits for pain-related complaints are rising (1). Subjects with chronic pain account for 12-16% of total ED visits (2,3) with 7% of subjects with chronic pain presenting multiple times (4). Both the Department of Health and Human Services (HHS) and the Institute of Medicine (IOM) have identified pain as a significant public health problem in the United States (5). Currently, the vast majority of painful conditions within the ED are treated with either opioid or non-steroidal anti-inflammatory drug (NSAID) analgesic medications. Treatment of chronic pain syndromes in the ED can be particularly challenging, since many subjects with these conditions are tolerant to the effects of opioids and NSAIDs and it can therefore be difficult to control their pain exacerbations adequately in the emergency department solely with these medications

Ketamine [2-(o-chlorphenyl)-2-methylamino cyclohexanone] is a phencyclidine derivative with unique analgesic, amnestic, and dissociative properties that acts primarily as a competitive antagonist at the NMDA receptor within the limbic system to modulate autonomic responses to stimuli. Advantages of ketamine include its stable hemodynamic profile and lack of respiratory depression (unlike opioid medications). Ketamine is frequently used for moderate sedation in the ED; recently, it has been suggested that sub-dissociative dose ketamine (SDDK) may be used in the ED for successful primary treatment of acute exacerbations of chronic pain syndromes, or as an adjunct to opioids or NSAIDs. Such treatment has primarily been studied in pain clinic settings and thus far has not been evaluated in Page 1 of 11

Rev. 4/24/2018

an emergency department setting. We aim to determine whether the use of a sub-dissociative dose of ketamine may be effective in the treatment of acute exacerbations of chronic pain syndromes in subjects presenting to the emergency department.

Although the use of ketamine is currently accepted as standard care in the ED as a moderate sedation agent in both pediatric and adult populations (6-8), it has not been widely utilized for its specific analgesic qualities. While there is extensive evidence on SDDK's safety and efficacy within the anesthesia and palliative care literature, there is very little written about the use of SDDK within the ED setting. Most studies published thus far describe ketamine's use either for procedural sedation or in a palliative care setting, primarily among subjects with cancer-related pain, phantom limb pain, or other pain types (9-12). Indeed, very few studies specifically address SDDK's analgesic uses in the ED. There is promising evidence of SDDK's safe and effective use for the treatment of traumatic pain in the prehospital setting (13), and a randomized, double-blind trial demonstrated that SDDK was safe and reduced opioid consumption in trauma subjects (14-15). One retrospective case series noted SDDK's safe use in subjects presenting to the ED for medical pain (16). A randomized controlled trial compared SDDK to fentanyl as an adjunct to procedural sedation and found its side effect profile and analgesic properties to be superior to standard treatment (17-18). The use of SDDK has also been suggested as effective within wilderness and operational settings, with obvious applications to military populations (19).

6) Setting of the Human Research

This is a prospective, randomized, physician and subject blinded controlled clinical trial, conducted at Harbor UCLA Medical Center Emergency Department

7) Resources Available to Conduct the Human Research

This is a local research study to be conducted in the Emergency Department at Harbor UCLA Medical Center which treats 75,000 patients per year and is located in a brand new facility consisting of 80 beds. This study will include only adult patients and all patients for our study will be identified through triage when they are initially assessed. If they meet inclusion criteria they will be approached for possible enrollment in the study.

The PI and Co-investigators will devote approximately 3 - 4 hours per week conducting the trial during the time period from July 1, 2015 – June 30, 2016 and will should have no problem recruiting the required number of patients since pain is a the most common complaint to the Emergency Department. The Primary Investigator, [name], has conducted numerous research studies in the past. He has completed all required training to conduct research at this institution. He also is well-versed in the Federal regulations as he is a member of one of the institution's IRBs.

The coinvestigators, Drs. [name], [name] and [name] have assisted in conducting research studies in the past and will look to [name] and the LA BioMed Compliance Monitor for assistance and guidance in carrying out this study. They have also completed the training requirements to conduct research at the institution. [name] has assisted the investigators in the development of the study and will work directly with the senior investigators in carrying out the study. She has also completed the training requirements to participate in research at this institution.

Rev. 04/24/2018

We will make sure that all persons assisting with the trial are adequately informed about the protocol, research method, and their trial-related duties and functions.

The investigator and study team members will regularly meet to ensure that all persons assisting with the trial are adequately informed about the protocol, research method, and their trial-related duties and functions.

8) Prior Approvals

The study was originally submitted as unfunded and underwent peer review by the institute's Research Committee. Subsequently, [name] submitted a request for funding (grant) to the U.S. Air Force to support this research; he was awarded the grant in Aug. 2016.

9) Study Design

a) Recruitment Methods

Screening for eligibility will occur as follows:

Subjects who present to the Harbor UCLA Medical Center Emergency Department(ED) will be screened by the investigator and study team for possible eligibility for this study. Once a subject is identified we will meet with their treatment physician and review their medical record to see if they meet the inclusion criteria. A pregnancy test will be administered, after consent obtained, before the female subject is randomized.

b) Inclusion and Exclusion Criteria*

Inclusion Criteria:

- All adult subjects over the age of 18 with chronic pain* presenting to the emergency department with exacerbation of their chronic pain as their primary complaint
- Subjects who are willing and able to provide informed consent.
- * Chronic pain defined as greater > 3 months of symptoms and an initial VAS pain score > 70

Exclusion criteria:

History of overt psychosis, severe HTN as defined by SBP > 180 or DBP > 110, unstable angina, CAD, CHF, porphyrias, thyroid disease, seizure disorder, inability to provide informed consent: dementia, non-English/Spanish speakers, subjects in custody, suicidal, or clinically intoxicated.

c) Local Number of Subjects

We look to enroll a total of 106 subjects meeting the study criteria.

Protocol Modification 4/24/2018:

We are requesting the enrollment of an additional 10 subjects to the protocol. We initially asked to enroll 96 subjects and have thus far enrolled 80 and the recruitment has continued on schedule. In recent discussion with our statistician and co-investigator, [name], the original group size analysis of 96 (32 in each of three groups) did not account for potential loss of data or subjects withdrawing from the study and we should have asked initially for 106 subjects with the expectation of a 10% loss of data due to incomplete records or withdrawal of subjects in the study.

Rev. 04/24/2018

d) Study-Wide Number of Subjects*

This is a single center study done at the Harbor UCLA Emergency Department

e) Study Timelines*

Duration of an individual subject's participation in this study is 1 emergency department visit and one follow-up phone contact 24-48 hours after discharge from Emergency Department.

The estimated date for the start of enrollment of subjects will be September 2015, and it will be continued till the enrolled subjects' number reach the goal of 106.

f) Study Endpoints*

Primary endpoint: To compare pain relief between the 3 treatment groups as measured by the VAS. A decrease of at least 20mm on the VAS will be considered "significant" pain relief (20)

Secondary endpoint:

- (a) To compare total dosage of IV hydromorphone needed as rescue therapy to achieved adequate pain relief
- (b) To assess the risk for complications of sub-dissociative dose ketamine

g) Procedures Involved in the Human Research*

- 1. The informed consent process will be initiated by investigators in the emergency department.
- 2. All potential subjects will be informed that participation in the study could lead to a positive urine drug test that could remain positive for up to a month after the conclusion of the study.
- 3. Female subjects of child bearing age, will have a pregnancy test performed prior to enrollment; any subjects who are pregnant will be excluded from this project.
- 4. Each subject will be asked to grade his/her pain severity on a 100mm non-hatched visual analog scale (VAS) ranging from 0 (no pain) to 100 (worst, maximum pain).
- 5. Each subject will be asked to fill out a baseline pain questionnaire
- 6. Each subject will be placed on monitors for continuous pulse oximetry, Heart Rate, Respiratory Rate, and blood pressure every 5 minutes for the duration of the study of one hour and longer for any patient who needs continued care. The patients temperature will be taken prior to the start of the protocol..
- 7. Each subject will have an intravenous catheter placed.
- 8. Each subject will be sequentially assigned to one of three treatment groups, based on a computer-generated randomization schedule, to receive an intravenous infusion of sub-dissociative Ketamine (0.25mg/kg), sub-dissociative dose Ketamine (0.5mg/kg), or an equal amount of normal saline.
- 9. All medications will be prepared by an emergency department pharmacist and all study medication IV bags will be identical in appearance and will be administered by the emergency Page 4 of 11

Rev. 04/24/2018

department nurse caring for the patient who will be blinded to the study drug.

- 10. Each subject will receive lightly tinted sunglasses to wear during the duration of the study to minimize bias as ketamine can evoke a tell-tale short-lived nystagmus
- 11. Each subject will receive the study medication over a 20 minute period via an automated pump. At this point, the subjects will be asked to rate their pain on a VAS and asked if they need additional pain medication that will consist of intravenous hydromorphone with the dose and frequency determined by the discretion of the treating physician and documented on the data collection sheet.
- 12. After 1 hour the subject will again be asked to grade his/her pain on a VAS. Additionally, they will be asked if they experienced any other adverse effects over the treatment period, specifically: rash, hallucinations, anxiety, disorientation, burning at the injection site.
- 13. Subjects will be asked if they require additional pain relief. Those who request further pain relief will be administered hydromorphone IV, the dosage and frequency will be at the discretion of the treating physician. Total hydromorphone administration will be documented on the data collection sheet.
- 14. All subjects will receive a follow-up phone call from one of the investigators between 24 48 hours after their visit to the Emergency Department to gauge the extent of their continued pain through the use of a Pain Rating Scale. They will also be asked if they suffered any untoward effects and if so, will be asked to detail them.
- 15. Any study patient returning to the Emergency Department for any reason will be fully evaluated and the study team will be notified. If there is evidence of any psychotic reaction (persistent or delayed presentation after the administration of the medication, the patients will be treated with benzodiazepines (shown to be effective in the emergence reaction sometimes seen after dissociative doses of ketamine are used) and a psychiatric consult will be obtained. The medical monitor will also be notified because this would be an adverse event.

h) Data and Specimen Banking*

No data collected for banking purposes.

i) Data Management *

Descriptive statistics will be used. Tests for significance will be conducted using the t test for continuous variables and chi-squared test or Fisher's exact test for categorical variables.

We estimated the sample size needed for the primary end point of significant pain relief as defined by a decrease in the VAS of 20mm. A power analysis based indicated that a sample size of 106 subjects would be required to detect a statistically significant difference with a power of 90% ($\alpha = 0.05$).

Data from the patient examinations will be stored in an excel spreadsheet or compatible REDCAP database after being de-identified of all unique information to the subject. The study source documents (including consent forms, etc.) will be stored in a locked filing cabinet in a locked office only accessible by study investigators. It will be stored until this

Rev. 04/24/2018

study completes. The data will be shared among the principal investigator and coinvestigators. Principal investigator will be responsible for receipt or transmission of the data.

Protocol Modification 4/24/2018:

We are requesting the enrollment of an additional 10 subjects to the protocol. We initially asked to enroll 96 subjects and have thus far enrolled 80 and the recruitment has continued on schedule. In recent discussion with our statistician and co-investigator, [name], the original group size analysis of 96 (32 in each of three groups) did not account for potential loss of data or subjects withdrawing from the study and we should have asked initially for 106 subjects with the expectation of a 10% loss of data due to incomplete records or withdrawal of subjects in the study.

j) Confidentiality

Confidentiality will be maintained by use of coded data sheets and an enrollment logbook. Data will be stored in a password locked excel data sheet s/REDCAP database. The study source documents (including consent forms, etc.) will be stored in a locked filing cabinet in a locked office only accessible by study investigators. It will be stored until the completion of this study. Only research investigators and research associates will have an access to this data or the room where the data sheets and enrollment logbook is kept.

k) Provisions to Monitor the Data to Ensure the Safety of subjects*

[name], an Emergency Physician not associated with the study but who has an expertise in procedural sedation in emergency department patients will be a Safety Monitor who will review all patient information whether they received placebo or ketamine for both harm and benefit on a monthly basis to determine if the study is safe to continue. [name], is an LAbiomed investigator with significant experience in the conduct of research and possesses the expertise to serve as the Safety Monitor.

l) Withdrawal of Subjects*

Subjects will be withdrawn from the study if they don't complete their Ketamine or normal saline infusion and they will continue to be monitored and treated as necessary if they experience any untoward or unexpected effects from the medication.

10) Risks to Subjects*

Risk of Ketamine

Incidence unknown: Bloody or cloudy urine, bluish lips or skin, blurred vision, chest pain or discomfort, confusion, disorientation, convulsions, cough, increased secretions, dizziness, syncope, tachycardia, hives, itching, facial edema, hallucinations, rash, agitation, anxiety, fatigue, unmasking psychosis

Risk of Sodium Chloride

Common: None Uncommon: Edema

Rare: Congestive Heart Failure from fluid overload

Risk of intravenous catheter insertion

Uncommon: bruise at the puncture site, inflamed vein

Rare: Infection

Page 6 of 11

Rev. 04/24/2018

The study involves the collection and recording of information including protected health information. There is a slight risk of a breach of confidentiality.

Subjects will be asked to rate their pain throughout the study which may cause them some anxiety.

11) Potential Benefits to Subjects*

Possible pain relief. If randomized to placebo (saline solution) subjects pain is monitored and pain relief provided if pain is not subsiding.

12) Provisions to Protect the Privacy Interests of Subjects

Data confidentiality is maintained as above. Only research investigators will have an access to this data.

The enrollment will be performed at emergency department.

We will not discuss private medical information in a setting with other than a health care provider or in other than a private clinical setting.

For the follow up phone call, we will ascertain from the subject, that they are willing and able to any questions and that they feel they have adequate privacy to do so.

We will limit the information being collected to only the minimum amount of data necessary to accomplish the research purposes.

13) Compensation for Research-Related Injury

There is no commitment to provide any compensation for research-related injury. In the event that subjects are injured as a result of participating in this research, emergency care will be available. But subjects will, however, be responsible for the charges for the emergency care.

14) Economic Burden to Subjects

The cost for the care provided during the emergency department visit is the responsibility of the subject. The subject will not be charged for the study medication (ketamine or saline).

15) Consent Process

Consent process will take place in the Emergency Department. Patients will be presented with the risks and benefits of participating in the study when being introduced to the study. During the consent process, patients will be asked to explain to the investigator or research associates the following aspects of the study, based on the UC San Diego Brief Assessment of Capacity to Consent (UBACC): What is the purpose of the study? What makes you want to participate in the study? Do you have to be in the study if you do not want to participate? If you withdraw from the study, will you be able to receive regular treatment? Please describe some of the risks and discomforts for being part of this study? If patients are unable to answer the questions with an appropriate, or correct response, they will be informed of the correct response, and will not be able to proceed unless they are able to express, in their own words, the correct, or appropriate, response.

Page 7 of 11

Rev. 04/24/2018

If subjects require some time for the information to be absorbed and appreciated, the researcher allow a period of time to elapse between imparting the information and requesting a signature on the consent form.

We are following "SOP: Informed Consent Process for Research (HRP-090)."

Non-English Speaking Subjects

Other than English, we expect Spanish speaking population to be participated in the study. In such case, consent form written in Spanish will be provided, and we will provide oral information using language line or by Spanish speaking investigators.

Subjects who are not yet adults (infants, children, teenagers)

Only subjects over the age of 18 will be included in this study.

Cognitively Impaired Adults

Only subjects capable of consent will be included in this study. The UBACC will utilized as described above.

Adults Unable to Consent

Only subjects capable of consent will be included in this study.

16) Process to Document Consent in Writing

We have reviewed and will follow "SOP: Written Documentation of Consent (HRP-091)."

17) Vulnerable Populations

Adults unable to consent, individuals who are not yet adults, pregnant women, and prisoners will be excluded in this study.

Other vulnerable subjects, such as students, subjects with limited or no treatment options, and socially and economically disadvantaged, may be included in this study. This study does not involve more than minimal risk to the subject.

18) Drugs or Devices

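### Ketamine complications: the only scheduled symptom question in the ED comes at 1 hour, after rescue hydromorphone may have been given, without onset timing and from a short list, so drug effects may be confounded and some under-counted

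*Combined protocol and SAP*

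**What the plan says.** Section 9 f) gives secondary endpoint (b) as: "To assess the risk for complications of sub-dissociative dose ketamine". It defines no complication, time window or grading.

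The timing comes from section 9 g):

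- Step 11: "Each subject will receive the study medication over a 20 minute period via an automated pump". At that contact subjects give a VAS and are "asked if they need additional pain medication that will consist of intravenous hydromorphone". Dose and frequency are left to the treating physician and documented. No adverse-effect question is scheduled.
- Step 12, at 1 hour: after a further VAS, subjects are "asked if they experienced any other adverse effects over the treatment period, specifically: rash, hallucinations, anxiety, disorientation, burning at the injection site".
- Step 6 provides "continuous pulse oximetry, Heart Rate, Respiratory Rate, and blood pressure every 5 minutes for the duration of the study of one hour".
- Step 14, the call at 24 to 48 hours: "They will also be asked if they suffered any untoward effects and if so, will be asked to detail them".

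Section 10 lists the risks of ketamine, among them "confusion, disorientation, convulsions, cough, increased secretions, dizziness, syncope, tachycardia". Section 9 i) names chi-squared or Fisher's exact tests for categorical variables and says nothing on rescue or onset. Section 4 hypothesises that with ketamine "subjects will require overall less opioid pain medications for adequate pain relief".

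**The concern.** The endpoint is about ketamine, but by 1 hour a subject may have had two active drugs. A symptom reported then cannot be placed before or after hydromorphone from what the protocol says is asked. The trial's own hypothesis is that opioid exposure differs by arm, so the second drug need not cancel out between arms.

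The named list is also narrow against the protocol's own risk list. Effects outside it depend on the subject volunteering them.

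At stake is how far the complication result can be attributed to ketamine. In a trial of this size it could look more reassuring than it should, and the data would not show whether it does.

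**Working it through.** **Plan's own figure.** None is given for this endpoint. The sample size in section 9 i) is for the VAS endpoint: 96 = 3 × 32, and 96 × 1.10 = 105.6, which rounds up to 106, or about 35 per arm. That step reproduces, but no power is claimed for complications.

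**List coverage.** Section 10 gives 21 ketamine items. Step 12 names four of them (rash, hallucinations, anxiety, disorientation) plus injection-site burning. That leaves 21 − 4 = 17 unprompted. Six that a subject could readily report are dizziness, confusion, agitation, blurred vision, itching and fatigue.

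**Effect of asking after rescue.** Every rate here is assumed, because the documents give none. Let p be the symptom rate before rescue, r the share of the arm rescued before 1 hour, and q the chance that hydromorphone causes the symptom in a rescued subject. With independent effects:

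rate at 1 hour = p + (1 − p) × r × q

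Take p = 0.10 (saline) and 0.40 (one ketamine arm), with r = 0.70 and 0.40. Then saline = 0.10 + 0.63q and ketamine = 0.40 + 0.24q. Power is for Fisher's exact test, two-sided 0.05, 35 per arm.

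| q | Saline | Ketamine | Difference | Power |
|---|---|---|---|---|
| 0 | 10.0% | 40.0% | 30 points | 78% |
| 0.05 | 13.2% | 41.2% | 28 points | 69% |
| 0.10 | 16.3% | 42.4% | 26 points | 59% |
| 0.20 | 22.6% | 44.8% | 22 points | 42% |
| 0.30 | 28.9% | 47.2% | 18 points | 27% |

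At 32 per arm (before the loss allowance), a normal approximation gives 81%, 64%, 47% and 32% for q = 0, 0.10, 0.20 and 0.30: the same pattern.

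**Direction.** The change in the difference is q × [(1 − p_ketamine) × r_ketamine − (1 − p_saline) × r_saline].

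- Equal rescue, 0.50 in each arm: q × (0.30 − 0.45) = −0.15q. The difference is 28.5 points at q = 0.10 and 25.5 at q = 0.30. Some dilution remains because fewer saline subjects already have the symptom.
- Rescue reversed, 0.40 saline and 0.70 ketamine: q × (0.42 − 0.36) = +0.06q. The difference widens slightly, to 31.8 points at q = 0.30.
- If ketamine and opioid together cause more symptoms than independence implies, the difference could also widen.

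**Effect of the short list.** Suppose the question captures a fraction s of all symptomatic subjects in both arms. The difference is then s × 30 points: 22.5 at s = 0.75 and 15 at s = 0.50. Power at 32 per arm (normal approximation) goes from 81% to 64% and 44%. The values of s are assumed.

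**Other safety capture.** Vital signs and oximetry do not record subjective symptoms. The phone call is open-ended but also follows any rescue. The Safety Monitor's monthly review (section 9 k) works on data already collected. None of these establishes the order of symptom and hydromorphone.

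**The case against.** A reader might infer that the comparison is diluted as a matter of fact and biased towards no harm. The documents do not support that. They give no rescue rate and no rate at which hydromorphone causes the five named effects. If it causes none, nothing is diluted, and an interaction could push the other way.

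The 1-hour comparison is also a valid randomised comparison of ketamine plus rescue as needed against saline plus rescue as needed. Fewer opioid effects because less opioid was needed would be a real consequence of ketamine. This stands, although endpoint (b) is worded about ketamine itself.

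The step 12 question looks back over the whole treatment period, so it covers the infusion, and its opening words could be read as open-ended. That limits the under-counting argument but does not date a symptom. The data collection sheet is not in the documents, so it may record onset. Some unlisted effects overlap listed ones, such as confusion with disorientation.

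A second tempting step is to replace the 1-hour comparison with 20-minute answers. That would drop effects arising between 20 and 60 minutes, although step 15 itself anticipates delayed reactions. Symptom answers before a discretionary rescue decision could also hint at allocation, which the sunglasses in step 10 are meant to conceal. And with 80 of 106 enrolled at the 4/24/2018 revision, at most 26 subjects remain, about 9 per arm. At 40% versus 10%, Fisher power is then about 14%. These objections stand and shape the fix.

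**Conclusion.** The point holds as a risk of confounding and under-counting. The protocol schedules no symptom question before rescue, asks for no onset time, and prompts for four of its own 21 listed ketamine risks. Existing monitoring does not separate the two drugs.

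The size cannot be stated from the documents. Under the assumed 10% and 40% pre-rescue rates and 70% and 40% rescue, the loss runs from nothing at q = 0 to about 12 points at q = 0.30. The direction is towards no difference only if the saline arm receives enough additional hydromorphone and hydromorphone causes the queried symptoms. The power figures are illustrative, for an endpoint with no stated power, and compare one ketamine arm with saline. The primary endpoint is not affected. This is a cheap improvement to a secondary safety endpoint, not a flaw that invalidates the randomised comparison.

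**What to change.** In step 11, once the 20-minute VAS and the rescue question have been answered and before any hydromorphone is given, have study staff record an adverse-effect checklist. It should hold the five step 12 items, the six reportable section 10 effects (dizziness, confusion, agitation, blurred vision, itching, fatigue) and one open question. Staff should not pass the answers to the treating physician unless safety requires it. Repeat the same list at 1 hour, after the VAS, and record whether each effect began before or after hydromorphone. No treatment rule changes.

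For endpoint (b), keep the randomised 1-hour comparison as the overall complication result. Report the pre-rescue answers beside it as the comparison attributable to ketamine. Treat any split by hydromorphone received as descriptive, because it conditions on something that happens after randomisation.

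The cost is a revised data sheet, about a minute more per subject at an existing contact, and a small risk to the blind. Counting from the 4/24/2018 revision, only the remaining subjects (at most 106 − 80 = 26) could supply pre-rescue data. Report these descriptively and separately from subjects asked only the current list. For the latter, show the 1-hour effects alongside the documented hydromorphone, descriptively, and state the limitation.

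### The 1-hour symptom checklist has no described pre-infusion counterpart and no new-or-worse rule, so pre-existing anxiety may be reported as a complication in any arm and dilute the ketamine-saline difference

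*Combined protocol and SAP*

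**What the plan says.** Secondary endpoint (b) in section 9(f) reads "To assess the risk for complications of sub-dissociative dose ketamine". It gives no event definition, expected rate or effect size.

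The main source of data for it is section 9(g), step 12. After 1 hour, subjects are asked whether they "experienced any other adverse effects over the treatment period, specifically: rash, hallucinations, anxiety, disorientation, burning at the injection site". Step 14 adds an open question about untoward effects at the follow-up call.

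Before the infusion, steps 3 to 6 describe a pregnancy test, a pain VAS, monitoring of vital signs with a temperature reading, and one form: "Each subject will be asked to fill out a baseline pain questionnaire". The items of that form are not shown.

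Several other provisions bear on the point:
- Section 9(b) requires an initial VAS above 70. Its exclusions include "History of overt psychosis, severe HTN as defined by SBP > 180 or DBP > 110" and "inability to provide informed consent: dementia, non-English/Spanish speakers, subjects in custody, suicidal, or clinically intoxicated".
- Section 15 adds a capacity check: a subject who answers wrongly "will not be able to proceed unless they are able to express, in their own words, the correct, or appropriate, response".
- Section 9(i) names the chi-squared and Fisher's exact tests for categorical variables, with no adjustment for baseline.
- Section 10 lists anxiety, disorientation and hallucinations among ketamine's risks and gives their incidence as unknown.

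**The concern.** Endpoint (b) is about risk attributable to the study drug. Anxiety is on the checklist, and a person in the emergency department with severe pain can be anxious before any drug is given. If that anxiety persists through the infusion, a truthful answer at 1 hour can be yes, and nothing in the plan separates it from new anxiety.

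Two things follow. The rate within each arm no longer measures what the drug did. This matters because section 10 treats ketamine's rates as unknown, so readers will look to this trial for them. The contrast with saline is also weakened, because a subject who reports pre-existing anxiety is counted as a case under either treatment and contributes nothing to the difference.

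**Working it through.** **The plan's own figure.** The documents give a sample size for the primary endpoint only. Section 9(c) has 3 × 32 = 96 subjects, raised for 10% loss: 96 × 1.10 = 105.6, so 106. That reproduces. (Dividing instead gives 96/0.90 = 106.7, so 107; the difference is immaterial here.) There is no stated power for complications to reproduce. The evaluable number per arm is therefore taken as 32.

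**Model.** Let b be the share of each arm that has the symptom before infusion and reports it at 1 hour, and let e be the new-onset risk among the others.

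- Reported rate = b + (1-b)e
- Reported risk difference = (1-b)(e_ketamine - e_saline)

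Randomisation makes b equal across arms in expectation, so the difference shrinks but keeps its sign.

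**Inputs.** From the documents: 32 per arm and Fisher's exact test. Assumed: e = 5% for saline and 30% for one ketamine arm, two-sided alpha 0.05 for that single comparison, every pre-existing symptom reported, and the range of b.

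| b | Saline reported | Ketamine reported | Difference | Exact Fisher power |
|---|---|---|---|---|
| 0 | 5% | 30% | 25 points | 68% |
| 2% | 0.02 + 0.98 × 0.05 = 6.9% | 0.02 + 0.98 × 0.30 = 31.4% | 24.5 points | 62% |
| 10% | 0.10 + 0.90 × 0.05 = 14.5% | 0.10 + 0.90 × 0.30 = 37% | 22.5 points | 45% |
| 20% | 0.20 + 0.80 × 0.05 = 24% | 0.20 + 0.80 × 0.30 = 44% | 20 points | 31% |

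The row b = 2% is an assumed value for hallucinations and disorientation after the exclusions. The rows at 10% and 20% are possible values for anxiety. The absolute saline rate is hit hardest: at b = 20% it is nearly five times the new-onset rate (24/5 = 4.8), while the difference loses a fifth.

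**What a new-or-worse rule would recover**, if every subject had the baseline item. Everyone stays in the denominator. In the least favourable case no pre-existing symptom ever worsens, and the rates are (1-b)e:
- At b = 10%: 4.5% against 27%, power 60%.
- At b = 20%: 4% against 24%, power 50%.

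In the most favourable case existing symptoms worsen at the same risk as new ones arise. The rates return to 5% against 30%, and power to 68%.

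**Who can still get the item.** 106 - 80 = 26 subjects, about 9 per arm. Pooled across arms, 26 subjects estimate a prevalence of 20% with standard error √(0.20 × 0.80/26) = 0.078, or roughly ±15 points.

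**The case against.** Step 12 asks about adverse effects during treatment, which already points subjects towards what happened after the infusion began. Carry-over therefore depends on how they answer. If only half of the pre-existing symptoms were reported, b = 20% would act like b = 10%, and saline would show 14.5% instead of 24%. This stands: the plan allows carry-over but does not make it certain. The wording limits when the symptom was present, not whether it is new.

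Two of the symptoms are largely screened out. The exclusions for psychosis, dementia, intoxication and inability to consent, together with the teach-back, leave little room for hallucinations or disorientation at entry. This also stands, and the point rests mainly on anxiety, which nothing in section 9(b) or 15 screens for.

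The randomised, blinded saline arm shows the background rate. A reader might infer that ketamine's effect is masked. The documents do not support that, because the contrast is diluted by (1-b) and not hidden or reversed. The saline arm does not undo the dilution, however, and cannot show which subjects had new symptoms.

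A reader might also take the section 10 sentence, "Subjects will be asked to rate their pain throughout the study which may cause them some anxiety", as evidence of anxiety before treatment. It concerns anxiety arising from study procedures as they go on. A baseline question would not remove that, and the saline arm is the right control for it.

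Finally, the questionnaire at step 5 may contain an anxiety item; its content is not shown. Even so, no stated rule would use it.

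**Conclusion.** The point holds as a minor one. The step 12 symptoms are not described as recorded before infusion, and no rule restricts endpoint (b) to new or worse symptoms. Pre-existing anxiety may therefore raise absolute rates in all arms and shrink the ketamine-saline difference by about (1-b).

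The size cannot be derived from the documents. Under the assumed 30% against 5%, with 32 per arm and full reporting of pre-existing symptoms, power falls from 68% to 45% at b = 10% and to 31% at b = 20%. At b = 2% it is 62%, so hallucinations and disorientation are little affected. Incomplete reporting would make the loss smaller.

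It would go too far to say that existing symptoms are certainly counted, or that a baseline item would restore the lost power in this trial: 80 of 106 subjects were enrolled before it could be added. The primary VAS endpoint is untouched.

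**What to change.** At step 5, before the infusion, ask the step 12 items that can already be present (rash, hallucinations, anxiety, disorientation), each graded none, mild, moderate or severe. Grade them the same way at 1 hour, so that worsening can be seen. In section 9(f), define a complication for endpoint (b) as a symptom that is new or worse than this baseline. Report baseline prevalence by arm. Burning at the injection site needs no baseline item, since it belongs to the infusion.

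The cost is four short questions, a severity grade at step 12 and one sentence in 9(f). Asking beforehand may slightly prime reporting, equally in all arms. Subjects enrolled before the change lack the item and must be shown separately. For them the gain is limited to an estimate of background prevalence, taken from later subjects, against which to read their rates. If the existing questionnaire already records anxiety, the definition could be applied to that item for all subjects.
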